5.1.3 Handling and Processing of Specimens

PK: The blood samples will be placed immediately on wet ice and refrigerated. The date and exact time of each blood draw should be recorded on the sample tube and the PK sheet. Tumor samples for PK and PD evaluations will be picked up from the Laboratory of Pathology by the NOB staff and transported to NOB Laboratory in Building 37. Tissues procured at various time points will be divided. Material for PD studies will be frozen in NOB Laboratory and remaining tissue for PK evaluation will be sent to the [name] Laboratory.

Please e-mail [contact] at least 24 hours before transporting samples (the Friday before is preferred).

For sample pickup, page [name].

For immediate help, call [contact] (main blood processing core number) or, if no answer, [contact] (main clinical pharmacology lab number).

For questions regarding sample processing, contact [contact].

Upon arrival in the Clinical Pharmacology Program, samples will be centrifuged and the plasma transferred into cryovials for storage at -80 C until the time of analysis. In addition, samples will be barcoded as described in Section **5.2.2.1**.

- 5.1.3.1 PD: Tumor tissues will be frozen in a -80 freezer in the NOB Laboratory until time of analysis. For PD studies on blood, PBMC will be retrieved from the [name] Laboratory.
- 5.1.3.2 Tissue blocks can be shipped to Department of Pathology at NCI at the following address:

Laboratory of Pathology
Center for Cancer Research
National Cancer Institute
[name]
[name]
Ph: [contact]

5.2 SAMPLE STORAGE, TRACKING AND DISPOSITION

5.2.1 Tissue blocks

5.2.1.1 Laboratory of Pathology

Paraffin embedded tissue block will be stored at Laboratory of Pathology located at building 10. Tissues designated for clinical diagnostics are transported to the Laboratory of Pathology (LP) where they are examined grossly and relevant portions are fixed, embedded in paraffin and sectioned and stained for diagnostic interpretation. Unutilized excess tissues are stored for up to three months, in accordance with College of American Pathologists/Joint Commission on Accreditation of Healthcare Organizations (CAP/JCAHO) guidelines, and then discarded. Following completion of the diagnostic workup, the slides and tissue blocks are stored indefinitely in the LP's clinical archives. All specimens are catalogued and retrieved utilizing the clinical laboratory information systems, in accordance with CAP/JCAHO regulations. The use of any stored specimens for research purposes is only allowed when the appropriate IRB approval has been obtained. In some cases, this approval has been obtained via the original protocol on which the patient was enrolled.

5.2.1.2 NOB Laboratory (PD Studies)

Samples will be ordered in CRIS and tracked through the Clinical Trial Data Management system. Should a CRIS screen not be available, the CRIS downtime procedures will be followed. Samples will not be sent outside NIH appropriate approvals and/or agreements, if required.

All samples sent to the Neuro-Oncology, Pathology Laboratory or the Brain Tumor Tissue Bank will be barcoded with data entered and stored in the Labmatrix system utilized by the CCR, NCI. This is a secure system with access limited to defined personnel.

Labmatrix creates a unique barcode ID for every sample which cannot be traced back to patients without Labmatrix access. The data recorded for each sample includes the patient ID, name, trial name/protocol number, date/time drawn, as well as box and freezer location. Patient demographics associated with the Clinical Center patient number are provided in the system. For

each sample, there are notes associated with the processing method (delay in sample processing, storage conditions on the ward, etc.).

These freezers are located onsite located in [name]. The freezer remains locked and access to stored clinical samples is restricted. Samples will be stored at -80° C in freezers with electronic monitoring. Samples will be stored until requested by a researcher named on the protocol. All requests are monitored and tracked in the Labmatrix System. All researchers are required to sign a form stating that the samples are only to be used for research purposes associated with an IRB approved protocol and that any unused samples must be returned to the NCI. It is the responsibility of the NCI Principal Investigator to ensure that the samples requested are being used in a manner consistent with IRB approval.

5.2.2 Pharmacokinetic samples

Samples for this study will be collected and stored by the Sample Processing Core. Bioanalytical measurements will be conducted on an ultra HPLC-MSMS system using an assay developed and validated by the Clinical Pharmacology Program.

Clinical Pharmacology Contact for Processing: [contact]

5.2.2.1 Sample Data Collection

All samples sent to the Blood Processing Core (BPC) will be barcoded, with data entered and stored in Labmatrix utilized by the BPC. This is a secure program, with access to Labmatrix limited to defined [name] lab personnel, who are issued individual user accounts. Installation of Labmatrix is limited to computers specified by [name]. These computers all have a password restricted login screen.

Labmatrix creates a unique barcode ID for every sample and sample box, which cannot be traced back to patients without Labmatrix access. The data recorded for each sample includes the patient ID, name, trial name/protocol number; time drawn, cycle time point, dose, material type, as well as box and freezer location. Patient demographics associated with the clinical center patient number are provided in the system. For each sample, there are notes associated with the processing method (delay in sample processing, storage conditions on the ward, etc.).

Following completion of this study, samples will remain in storage as detailed above. Access to these samples will only be granted following OHSRP/IRB approval of an additional protocol, granting the rights to use the material or if the use is not considered to be human subjects research.

5.2.3 Sample Storage and Destruction

All specimens obtained in the protocol are used as defined in the protocol. Any specimens that are remaining at the completion of the protocol will be stored in the conditions described above. The study will remain open so long as sample or data analysis continues. Samples from consenting subjects will be stored until they are no longer of scientific value or if a subject withdraws consent for their continued use, at which time they will be destroyed.

If the patient withdraws consent the participant's data will be excluded from future distributions, but data that have already been distributed for approved research use will not be able to be retrieved.

The PI will record any loss or unanticipated destruction of samples as a deviation. Reporting will be per the requirements of section **7.2**.

6 DATA COLLECTION AND EVALUATION

6.1 DATA COLLECTION

The PI will be responsible for overseeing entry of data into a 21 CFR Part 11-compliant data capture system provided by the NCI CCR and ensuring data accuracy, consistency and timeliness. The principal investigator, associate investigators/research nurses and/or a contracted data manager will assist with the data management efforts. Primary and final analyzed data will have identifiers so that research data can be attributed to an individual human subject participant.

All adverse events, including clinically significant abnormal findings on laboratory evaluations, regardless of severity, will be followed until return to baseline or stabilization of event.

Document adverse events from the first study intervention, Study Day 1 through Study Day 30 (safety visit). Beyond 30 days after the last intervention, only adverse events which are serious and related to the study intervention need to be recorded.

For patients whose pathological evaluation at craniotomy demonstrates treatment effect (e.g. necrosis or inflammation as a result of therapy) rather than tumor recurrence, adverse events will still be monitored from the first study intervention, Study Day 1 through Study Day 30 (safety visit).

Grade 1 events need not be captured, collected, or reported.

An abnormal laboratory value will be recorded in the database as an AE **only** if the laboratory abnormality is characterized by any of the following:

- Results in discontinuation from the study
- Is associated with clinical signs or symptoms
- Requires treatment or any other therapeutic intervention
- Is associated with death or another serious adverse event, including hospitalization.
- Is judged by the Investigator to be of significant clinical impact
- If any abnormal laboratory result is considered clinically significant, the investigator will provide details about the action taken with respect to the test drug and about the patient's outcome.

End of study procedures: Data will be stored according to HHS, FDA regulations and NIH Intramural Records Retention Schedule as applicable.

Abbreviated Title: Phase II Study LB100 gliomas

Version Date: 06/02/2022

Loss or destruction of data: Should we become aware that a major breach in our plan to protect subject confidentiality and trial data has occurred, this will be reported expeditiously per requirements in section **7.2.1**.

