1.2.4 LB100 Phase I Study

A phase I, open label, single center, two-part, dose-escalation study of LB100 administered intravenously in patients with advanced solid tumors was conducted at City of Hope National Medical Center. The objectives of the study were to determine the: 1) Safety and tolerability; 2) Maximum tolerated dose (MTD); 3) Pharmacokinetics (PK). Study reached its accrual goal and closed to further patient enrollment on 5/20/2016. Dose limiting toxicity (DLT) was reversible decrease in creatinine clearance at the maximum administered dose of 3.1 mg/m^2 ; no other toxicities were reported. Additional patients were enrolled at a lower dose of 2.33 mg/m^2 . This dose was well tolerated without creatinine elevation, and determined to be the recommended

Abbreviated Title: Phase II Study LB100 gliomas

Version Date: 06/02/2022

phase II dose. On-going PK evaluation on the first cohort of subjects suggest a LB100 half-life of ~1.3 hours.

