3.3 FOLLOW-UP

All patients will be evaluated in person 1-3 days following craniotomy and followed for at least 30 days after infusion of LB-100 for toxicity assessment. During the first week after infusion with LB-100, renal function tests and liver function tests will be performed. Two to 3 weeks following discharge from the hospital, all patients will return to the clinic or be seen by their local physician for a physical exam and bloodwork. Given that the methodologies utilized are similar across all laboratories, no significant variability is expected and there is no anticipation that study data will be affected. Patients will be contacted by phone (or seen in clinic) at approximately 30 days post craniotomy and will be asked a non-leading question to determine whether any new AEs have occurred and to follow up on any ongoing AEs.

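### The section 6.1 laboratory filter could leave a reversible creatinine rise out of the adverse-event record, and section 10 plans no creatinine summary

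*Combined protocol and SAP*

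**What the plan says.** **Recording rule (section 6.1).** "An abnormal laboratory value will be recorded in the database as an AE" only when at least one listed condition holds: the patient discontinues; the abnormality "Is associated with clinical signs or symptoms"; it is treated; it accompanies death or another SAE; or the investigator judges its clinical impact significant. The same section adds that "Grade 1 events need not be captured, collected, or reported".

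**Human experience (section 1.2.4).** "Dose limiting toxicity (DLT) was reversible decrease in creatinine clearance", seen at 3.1 mg/m², and "no other toxicities were reported". Of 2.33 mg/m² the section says: "This dose was well tolerated without creatinine elevation". Section 14.1.5 gives the Phase I regimen as three consecutive daily infusions every three weeks and states that this trial gives a single infusion.

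**Measurement (sections 3.3 and 3.4).** In the week after the infusion "renal function tests and liver function tests will be performed". The study calendar lists a laboratory panel that includes serum creatinine before treatment, at day 3 (plus or minus 2 days) and at weeks 2-3. The 24-hour creatinine clearance is done before treatment only, and only if eligibility requires it.

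**Analysis (section 10).** The planned analyses are PK response, PK parameters and PD response. No safety or laboratory analysis is listed.

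**The concern.** The filter suits abnormalities that are incidental to the drug. It fits less well where the laboratory value is itself the expected signal. The only toxicity seen in people was renal and reversible. The animal studies in section 14.1.2 also point to the kidney: rats developed nephrosis that persisted or progressed in males after recovery, and dogs had kidney changes still present at the day-29 necropsy. A mild renal effect in this trial might appear only as a change in serum creatinine.

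Section 12.4.1.1 says LB100 has not been given to glioma patients, and section 12.4.2 says participants gain no direct benefit. Whatever is reported about renal tolerability would come from an AE record that, for this type of event, depends on case-by-case judgement in an open-label study. No unfiltered summary of the measured values is planned beside it.

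The gap is sharpest for patients replaced because pathology shows treatment effect. Their PK and PD specimens are destroyed (section 5.1.2.11.1), but they have been dosed and are still followed for AEs (sections 3.7.2 and 6.1). No table covering all dosed patients is planned.

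**Working it through.** The plan states no figure on this point, so the check is mainly a reading of the text, followed by simple arithmetic.

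**Step 1. Put one event through section 6.1.** Suppose serum creatinine rises after the infusion, causes no symptoms, is not treated and returns to baseline.

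- Discontinuation: unlikely to apply, since there is one dose and it has already been given.
- Signs or symptoms, and treatment: not met, by construction.
- Death or another SAE: not met, unless something else happens, such as a prolonged hospital stay.
- Investigator judgement: may be met, but no renal threshold is given.
- Grade 1 sentence: a separate provision, under which a Grade 1 rise need not be captured.

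Judgement is therefore the only route left, and for a Grade 1 rise even that meets a second exclusion.

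**Step 2. Compare with other text.** The AE definition in 8.1.1 covers an abnormal laboratory finding, so it is wider than the filter. Section 6.1 also says that AEs are followed whatever their severity, and then relieves the site of capturing Grade 1. These statements need reconciling.

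**Step 3. Check whether the data exist.** They do: serum creatinine is scheduled at baseline, day 3 and weeks 2-3. The gap lies in recording and analysis. Because clearance is not repeated after dosing, serum creatinine is the available renal marker.

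**Step 4. Look for an analysis elsewhere.** Section 5.1.2.11.1 mentions correlating drug concentrations with toxicity, in general terms. Creatinine is not named.

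**Step 5. Size.** One unrecorded case among n dosed patients changes the observed rate by 1/n. The lower n is the five treated in stage one, after which the trial may stop. Eight is the evaluable target and 25 the enrolment ceiling.

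- n = 5: 1/5 = 20 percentage points
- n = 8: 1/8 = 12.5 points
- n = 25: 1/25 = 4 points

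**Step 6. Illustration under assumptions.** Let q be the true rate of such rises and c the share that investigators record. Neither is in the documents. The chance that at least one is recorded is 1 − (1 − q·c)^n. For example, with n = 8, q = 20% and c = 0.5 it is 1 − 0.9^8 = 57%.

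| n | q | c = 1 | c = 0.5 | c = 0.25 | c = 0 |
|---|---|---|---|---|---|
| 5 | 20% | 67% | 41% | 23% | 0% |
| 8 | 10% | 57% | 34% | 18% | 0% |
| 8 | 20% | 83% | 57% | 34% | 0% |
| 25 | 10% | 93% | 72% | 47% | 0% |

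Tabulating the measured values for all dosed patients corresponds to c = 1.

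**The case against.** The best case for leaving the plan alone has four parts.

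- **Exposure.** The renal toxicity arose at 3.1 mg/m², whereas Phase I saw no creatinine elevation at 2.33 mg/m². This trial gives one infusion, and the nephrosis in animals followed repeated daily dosing. This stands, and it lowers the expected number of events. It does not show that there will be none, and a statement of no renal effect would itself need the values.
- **Purpose.** Every objective is PK or PD, and no renal safety statement is planned. This stands and limits the weight of the point.
- **Oversight.** Renal tests are done in the first week, the principal investigator reviews each patient's AE data (7.4.1) and a safety committee reviews the protocol about once a year (7.4.2). This is real protection for patients, but the AE data reviewed have already passed through the filter. The values could be listed later, but nothing commits the trial to do so.
- **Confounding.** Some creatinine changes after a craniotomy will reflect surgery, and there is no control arm to separate causes. This stands and argues for a descriptive table without causal claims.

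A reader might also infer that the Phase I toxicity was itself free of symptoms and untreated, so that the filter would have missed it. Section 1.2.4 calls it reversible and reports no other toxicity. That is compatible with the inference but does not state it. Nor are Grade 1 events banned from the record: the wording is permissive.

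**Conclusion.** The point holds in a limited form. Section 6.1 could leave a reversible creatinine rise without symptoms or treatment out of the AE record, except through investigator judgement without a threshold. Section 10 has no creatinine summary to make up for it. This follows from the text and needs no assumption about event rates. The size per missed case is 1/n: 20, 12.5 or 4 percentage points at 5, 8 or 25 dosed. The recording probabilities are illustrative and depend on an assumed event rate and recording share.

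Two stronger readings are not supported. A reader might conclude that renal toxicity would be under-reported, or that the record is biased towards no effect. The documents show only that it could be, since investigators may record every such rise. A reader might also take the one-sided 95% upper bounds after zero recorded events as the size of the problem: 1 − 0.05^(1/5) = 45%, 1 − 0.05^(1/8) = 31%, 1 − 0.05^(1/25) = 11%. These measure how small the trial is and would be the same with perfect recording.

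Because no primary or secondary PK/PD analysis is affected, this is a change to consider. It bears on the completeness of the safety report.

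**What to change.** Reporting changes only:

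- **Section 6.1:** exempt post-dose increases in serum creatinine from both the conditional laboratory rule and the Grade 1 exclusion. Lifting only one would leave Grade 1 rises uncaptured.
- **Sections 6.1 and 8.1.1:** reconcile the filter with the AE definition, which includes abnormal laboratory findings.
- **Section 10:** add one descriptive table giving baseline, day-3 and week 2-3 creatinine, change from baseline and worst CTCAE grade for every dosed patient, including those replaced for treatment effect.

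The cost is a few sentences and one table, using blood already scheduled to be drawn. The drawback is a few more low-grade entries, some caused by surgery, which this single-arm trial cannot separate from drug effects. If the sponsor prefers to keep the AE filter as it is, the table alone would still give an unfiltered account of the measured values.

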6.2 DATA SHARING PLANS

6.2.1 Human Data Sharing Plan

What data will be shared?

I will share human data generated in this research for future research as follows:

- Coded, linked data in BTRIS (automatic for activities in the Clinical Center)
- Identified or coded, linked data with approved outside collaborators under appropriate agreements.

How and where will the data be shared?

Data will be shared through:

- BTRIS (automatic for activities in the Clinical Center)
- Approved outside collaborators under appropriate individual agreements.
- Publication and/or public presentations.

When will the data be shared?

- Before publication.
- At the time of publication or shortly thereafter.

6.3 RESPONSE CRITERIA

This is not a therapeutic protocol. Response will not be monitored.

6.4 TOXICITY CRITERIA

The following adverse event management guidelines are intended to ensure the safety of each patient while on the study. The descriptions and grading scales found in the revised NCI Common Terminology Criteria for Adverse Events (CTCAE) version 5.0 will be utilized for AE reporting. All appropriate treatment areas should have access to a copy of the CTCAE version

5.0. A copy of the CTCAE version 5.0 can be downloaded from the CTEP web site (http://ctep.cancer.gov/protocolDevelopment/electronic_applications/ctc.htm).

7 NIH REPORTING REQUIREMENTS/DATA AND SAFETY MONITORING PLAN

7.1 DEFINITIONS

Please refer to definitions provided in Policy 801: Reporting Research Events found at:

<https://irbo.nih.gov/confluence/pages/viewpage.action?pageId=36241835#Policies&Guidance-800Series-ComplianceandResearchEventReportingRequirements>.

Abbreviated Title: Phase II Study LB100 gliomas

Version Date: 06/02/2022

7.2 OHSRP OFFICE OF COMPLIANCE AND TRAINING /IRB REPORTING

7.2.1 Expedited Reporting

Please refer to the reporting requirements in Policy 801: Reporting Research Events and Policy 802 Non-Compliance Human Subjects Research found at:

<https://irbo.nih.gov/confluence/pages/viewpage.action?pageId=36241835#Policies&Guidance-800Series-ComplianceandResearchEventReportingRequirements>.

Note: Only IND Safety Reports that meet the definition of an unanticipated problem will need to be reported per these policies.

7.2.2 IRB Requirements for PI Reporting at Continuing Review

Please refer to the reporting requirements in Policy 801: Reporting Research Events found at:

<https://irbo.nih.gov/confluence/pages/viewpage.action?pageId=36241835#Policies&Guidance-800Series-ComplianceandResearchEventReportingRequirements>.

7.3 NCI CLINICAL DIRECTOR REPORTING

Problems expeditiously reported to the OHSRP in iRIS will also be reported to the NCI Clinical Director. A separate submission is not necessary as reports in iRIS will be available to the Clinical Director.

In addition to those reports, all deaths that occur within 30 days after receiving a research intervention should be reported via email to the Clinical Director unless they are due to progressive disease.

To report these deaths, please send an email describing the circumstances of the death to the Clinical Director/designee at [contact] within one business day of learning of the death.

7.4 NIH REQUIRED DATA AND SAFETY MONITORING PLAN

7.4.1 Principal Investigator/Research Team

The clinical research team will meet on a regular basis when patients are being actively treated on the trial to discuss each patient.

All data will be collected in a timely manner and reviewed by the principal investigator or associate investigators. Events meeting requirements for expedited reporting as described in section **7.2.1** will be submitted within the appropriate timelines.

The principal investigator will review adverse event and response data on each patient to ensure safety and data accuracy. The principal investigator will personally conduct or supervise the investigation and provide appropriate delegation of responsibilities to other members of the research staff.

